Title: TMS Related Biomarker Assessments

NCT number: NCT05660018

Document date: 01/18/2023

PI: [name], PHD

Study protocol

Background

Electrical neural oscillations of the brain can be measured at many levels, ranging from single cell to local field potentials in animals, to large-scale synchronized activities in the human scalp. New evidence suggests that there may be common underlying abnormalities in oscillatory activities that are associated with schizophrenia-related cognitive and functional impairments. There is currently no treatment for these electrical oscillation dysfunctions. Transcranial magnetic stimulation (TMS) provides a non-invasive means for altering brain electrical neural activity. TMS has been approved by FDA for the treatment of depression and many other mental disorders. It has been used in a wide range of clinical research, especially in neurology and psychiatry. The investigators aim to develop TMS paradigms that will modulate brain responses during basic sensory to more complex cognitive performance and determine the parameters in anatomic locations and TMS modalities that may effectively and safely modulate neural activities. If the current experiments successfully identified TMS methods/paradigms that improve neural oscillation and cognitive performances in schizophrenia patients, in the future (not part of the current protocol), the investigators can then develop specific TMS treatment that may correct abnormal brain function and improve cognition and clinical symptoms of schizophrenia.

The purpose of this research is to better understand how brain electric activities are changed during TMS. We will test the hypothesis that repetitive TMS pulses, such as theta-burst stimulations, and conventional low- and high-frequency stimulations (Huang et al 2005 *Neuron*; Williams et al 2018 *Brain*), will facilitate EEG neural oscillatory activities, cognitive behaviors, TMS-related responses, and fMRI brain circuitry measure improvement in schizophrenia patients.

Study Procedures

General TMS procedures: Motor threshold (MT): Motor threshold testing will start with around 50% intensity and an inter-stimulus interval (ISI) of about 0.2 Hz. The coil is moved in different directions and TMS intensity is gradually increased or decreased to find the site that most reliably elicits finger twitches. The intensity is then adjusted until about 5 of 10 consecutive pulses (100% MT) result in a finger twitch or finger muscular evoked potential (MEP). Motor evoked potential (MEP): MEP will be recorded from surface electrodes placed on one of the fingers. The minimal intensity required to elicit an EMG response of at least 50 uV with 50% probability in a fully relaxed muscle (Rossini et al., 1994) is the resting

motor threshold (RMT). We may mark the stimulation sites in the neural navigation system. During RMT tests, subjects are asked to keep their muscle relaxed. During active motor threshold (AMT) tests, subjects are instructed to make an isometric contraction between the thumb and index finger at certain percentage of maximum force before the TMS pulse. Subjects are instructed to relax, with head holding still or maintained by resting on chinrest. TMS will be administered using a Magstim or PowerMAG TMS machine. TMS single pulses are applied to the brain guided by the Brainsight (Rogue Research, Montreal, Canada) brain navigation system and the subject's anatomical MRI. The brain navigation system permits more precise TMS placement on the proposed anatomic regions. TMS will not exceed 120% magnetic field intensity relative to the patient's observed RMT. The TMS coils are fixed using a mechanical arm to keep the coil to scalp relationship constant throughout the experiment. Patient participants are required to give adequate responses on the Evaluation to Sign Consent (ESC) form prior to study entry to ensure that they understand the risks of the study and how to respond if they experience any distress or wish to withdraw from the study. A score of 10 or more out of the total possible score of 12 on ESC will meet the inclusion criteria.

MRI procedures: MRI will be done in a 3.0 Tesla magnet. During MRI, the subjects will perform resting and behavioral and cognitive tasks with visual and auditory presentations to be shown through a screen and head/ear phones. In some tasks the subject will be asked to simply rest, or to use a response pad. The specific tasks may include structural images for gray and white matter, resting scan, tasks that measure eye movement, motion perception and prediction, attention/working memory, learning and reversal learning tasks, finger tapping, and/or simple auditory and visual stimulus tasks. Each subject will perform only a subset of these tasks. Behavioral response, eye movement, basic physiological measures including breath, blood pressure, pulse, skin conductance can be recorded during imaging. Each subject will be inside the scanner for about 1 hour at different time of the rTMS treatment procedure. About four fMRI scans will be done in each sub-study. A repeat of scan is possible if other issues have led to incomplete or poor quality imaging data in previous scans. If a participant is not sure whether there are metal in their head or eye, for example past gunshot wound or involving in welding or metal drilling without eye protection, we may ask the participant to have a head x-ray of the head to make sure there is no metal in eyes or head before the MRI scan. The x-ray will involve a small amount of radiation, although the risk associated with a one-time x-ray is similar to any x-ray a doctor may prescribe during a clinic visit. They can refuse the x-ray and not participate in the MRI portion of the study. We may use some clinical assessments such as SCID done in other studies or previous clinical assessments if repeating them is not necessary. Similarly, data

collected here may be combined with data from other studies when appropriate. Data collected from this study may be combined with other related studies (e.g., brain imaging data collected from other protocols where combining data is stated) during data analyses. Subjects may not necessarily be excluded or withdrawn if they complete some but not all of the tests and assessments although we encourage them to complete all tasks.

EEG/ERP recording: subjects will be asked to wear a cap containing electrodes. Electrode paste will be used to facilitate the connection. Subjects may listen to sound stimulations by wearing a pair of headphones, hearing tubes, or through loudspeakers. Tests may include resting EEG, passive and active cognitive tasks. In resting EEG, subjects are asked to relax during brain wave recording. In brain wave recording during passive task: subjects may be asked to relax while sounds at different frequencies and durations are presented to elicit evoked potentials, which can be accompanied by visual presentations. No performance is required except to be alert. In brain wave recording for attention and memory tasks: subjects are asked to pay attention to auditory and visual stimuli while holding a response pad. They are trained and then perform the tasks by responding, remembering, or recalling certain items and ignoring the other items. These tasks are computerized auditory and visual stimuli and data are digitally recorded. Each test may last a few minutes to about half an hour; they are repetitive but with breaks between tasks to reduce subject fatigue. All recordings are stored in secure servers/computers using only a code.

TMS will be given in 2 sessions in 2 different days that are separated by one or more days. In one session you will receive active TMS. In another session you will receive sham TMS. The active or the sham TMS are delivered to one, two or three locations on your scalp. The TMS is given in about 4 minutes for each location. Therefore, in the active TMS day, you will receive 3 TMS administrations in three locations, one after another, for a total of about 12 minutes. In the sham TMS session, you may feel or hear similar TMS, but no actual TMS is stimulating your brain. TMS-evoked responses, brain waves, and MRI will be measured before and after each session to determine the TMS effects. It will take about 4 to 5 hours. It includes about 2 hours before and 2 hours after the TMS where we will perform clinical assessments, TMS-evoked responses, brain wave, and MRI assessments as described above. It also includes time to wear the electrode cap and remove the electrode cap and cleaning the hair after the experiment. About 30 participants will participate in this study.

Research Related Risks

General: There is a possibility of breaching of confidentiality. We plan to keep all your records confidential. Some of the procedures can cause boredom. In some of the interviews and questions we will be discussing and asking sensitive information (for example, feelings of sadness, unusual experience, alcohol use, mental illness in family members). You may feel embarrassed or distressed talking or giving out information. It is important to obtain accurate information from you to make the research valid and worthwhile. However, you can always stop and not participate without penalty. Our interviewers are experienced and should provide needed counseling.

TMS: TMS has been safely used in thousands of subjects at the US and throughout the world each year. Occasionally people may find the stimulations uncomfortable or even painful or causing headache, scalp or facial twitching or pain, or dental or muscle pain. If you find the procedure too uncomfortable you may discontinue it at any time. Headaches and pain usually go away promptly with over the counter pain medications. The magnetic pulse could heat up the scalp metal electrodes that could cause burning. The electrodes we use do not have metal that directly contacts the scalp. However, you should promptly inform the staff if you feel any increased heating. The skin stimulation sham electric pulses may cause skin discomfort, tingling, muscle twitching, headache or pain. As in real TMS, if you find the procedure too uncomfortable you may discontinue it at any time.

TMS can be loud and could cause temporary and, in one case, permanent decreases in hearing especially without hearing protection. You will be fitted with earplug or ear phones to wear during the study. This is to protect your hearing from the noise. You will sit in a position with minimal head motion. Sitting in a fixed position for a long time could be uncomfortable with possible body ache. There will be frequent breaks. You can ask for a break at any time.

Magnetic stimulation will not be performed in people who have pacemakers, implanted pumps or stimulators, or who have metal objects inside the eye or skull. Please inform the investigators if you have any of these conditions.

The most severe risk from TMS is seizure. The possibility that TMS used in this study will cause a seizure is very low. According to best current evidence, risk of seizures induced by

TMS is about <0.03%. A seizure has never resulted in permanent damage. Seizure, if induced by rTMS, occurs only during the application of stimulation. Beyond studies conducted specifically in patients with epilepsy, there has been no reported incidence of rTMS-associated seizure that had onset within hours or days after the stimulation procedure concluded. You will be carefully watched during each session. Staff is trained to promptly manage a seizure should one occur. Having a seizure could affect your future ability to drive, hold a job, or get insurance. Therefore, there may be financial risk with being in this study. Sleep deprivation, recent change in medication, alcohol consumption or too much caffeine intake may increase the risk of seizure. You might be at higher risk of having a seizure with TMS if you are taking clozapine. You will not be eligible for this study if you are taking >400mg clozapine daily. We will ask you to postpone the study if you had a recent change in certain medication, did not have a good night sleep, or consumed too many caffeinated drinks on the day of TMS or any alcohol within the 24 hours before TMS.

Other possible adverse events include fainting, nausea, changes in blood pressure and heart rate. If you feel you are not comfortable and weak, you should inform staff immediately, or you can stop at any time.

Another potential side effect from TMS treatment is changing of mood and occasionally other psychiatric symptoms such as increased psychosis, temporary changes in attention and memory. Heightened euphoria (mania) has happened to some people, most of whom had a history of mania or depression when they started TMS treatment.

The effects of TMS during pregnancy are unknown. If you are a female and are possibly pregnant (if you have child-bearing potential but are not taking contraceptives and missing menstrual period; or by your own report; or by positive a pregnancy test), you should not participate in this study. No one should enter the study that plans on fathering or conceiving a child between the times of study enrollment and completing the study. If you are female and are able to have children you must agree to use an approved birth control method. Acceptable birth control methods include the birth control pill, intrauterine device, or depot hormonal preparation (ring, injection implant). Correct use of a diaphragm, sponge with spermicide, or condom is also acceptable. We do not know if the experimental procedure affects fetal development.

MRI: The process itself is painless. There will be no x-rays or radioactivity in the MRI. However, you will be exposed to a high magnetic field. The magnetic field and radio waves used for MRI scans are considered too weak to do any damage to your body. However, nothing can be proven to be absolutely safe. There are potential side effects from the MRI scans. The first possible side effect is a mild backache from lying still for about one hour. You may experience claustrophobia, which is fear of small enclosed places. The MRI machine makes loud banging noises. You will be given earplugs or headphones that will lessen the sound. You may still experience some brief problems hearing soft sounds after the exam. Lying still for many hours may be a risk for the development of Deep Vein Thrombosis. This is blood clotting, usually in the legs, in persons with certain medical conditions. Persons with a history of thrombosis, family history of thrombosis, or medical conditions that may lead to an increased chance to develop blood clots cannot take part in this study. Please inform us immediately if you believe you should not take part for this reason.

Brain wave recording: A paste is used to attach the electrodes during brain wave testing, which may irritate the skin on the scalp or face. Irritation is mild and usually resolves quickly. We may ask you to not use hair products on the day of testing (or it has to be washed out prior to testing, which may be inconvenient). The electrode cap you wear can be tight and not comfortable, but it can be adjusted. The tasks can be quite long, boring, or even annoying. Some of the sounds can be loud and uncomfortable. We will give frequent breaks in-between. You can always ask for a break or re-schedule for another time to complete the study.

All safety measures to lessen any side effects will be taken. If you feel that you want to leave the study, you are free to do so at any time. If we feel that you should not continue, we will end the study. We may do this even if you do not want to end the study.

Because TMS is relatively new, its long-term effects are still unknown. We will monitor you at every visit. There may be risks in this study which are not yet known. You will be told of any new findings during the course of this study that may affect your participation. If you feel that you have an illness or symptoms related to your being in the study you should call us.

Statistical Analysis Plan

Demographics were compared using ANOVA or χ^2 tests. We will examine the differences in performances of biomarkers in active TMS compared to sham TMS. We will explore effects of age, sex, baseline medication, cognition, smoking status, and functional measures on biomarkers, and significant findings will be included as covariates. Exploratory analyses were conducted comparing active TMS vs. sham at different time points using independent-sample t-test and comparing baseline vs. post-TMS measurements using paired-sample t-tests at $p < 0.05$. Effect sizes were calculated for nominally significant measures using Cohen's d. All tests were two-tailed.

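### Refusing the metal-check x-ray removes an unsure participant from MRI only; no visible rule holds back TMS while possible eye or skull metal is unresolved (minor safety correction)

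*Combined protocol and SAP*

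**What the plan says.** The metal check is in the MRI procedures paragraph of Study Procedures. It is triggered "If a participant is not sure whether there are metal in their head or eye", with an old gunshot injury and unprotected welding or drilling as examples. Staff may then ask for a head x-ray, whose stated purpose is "to make sure there is no metal in eyes or head before the MRI scan". The consequence of declining is: "They can refuse the x-ray and not participate in the MRI portion of the study". The same paragraph ends by saying that people who complete only part of the tests and assessments need not be excluded or withdrawn.

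The TMS exclusion is in the TMS paragraph of Research Related Risks. Stimulation is ruled out for people with pacemakers or implanted pumps or stimulators, "or who have metal objects inside the eye or skull". Participants are asked to tell the investigators if any of these apply.

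Two other places bear on whether a refuser would reach TMS. General TMS procedures says "TMS single pulses are applied to the brain guided by the Brainsight (Rogue Research, Montreal, Canada) brain navigation system and the subject's anatomical MRI". The paragraph on the TMS sessions, which follows the EEG/ERP text, plans TMS-evoked responses, brain waves and MRI both before and after each session.

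**The concern.** Metal in the eye or skull matters for both MRI and TMS, and the protocol treats it as a reason to withhold either one. Yet the check for uncertain cases, and the consequence of declining it, are attached to MRI alone. The person concerned has a history that the protocol itself regards as suspicious, and cannot report a condition that he or she does not know about. Staff who follow the refusal sentence literally would cancel the scans and find nothing telling them to cancel the stimulation.

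What is at stake is the safety of an individual participant. The point has no bearing on the estimand, the analysis or the sample size.

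**Working it through.** No arithmetic applies, and the plan gives no figure to reproduce. The check is to apply every visible rule on metal, MRI and TMS eligibility to one case: a participant who is unsure about eye or skull metal and refuses the x-ray.

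1. **MRI procedures, x-ray rule.** It stops MRI. It does not mention TMS, and its timing is set by the scan ("to make sure there is no metal in eyes or head before the MRI scan").
2. **MRI procedures, partial completion.** Missing the MRI does not by itself require withdrawal, so the participant can remain in the study.
3. **Research Related Risks, TMS exclusion.** It applies to people who have the metal. Here that is unknown. The paragraph does not say how to treat unknown status, and its only stated means of detection is the participant's own report.
4. **Research Related Risks, other TMS stops.** The text excludes people on more than 400 mg of clozapine daily. It postpones TMS for certain recent medication changes, poor sleep, excess caffeine, or alcohol in the previous 24 hours. Unresolved metal is not listed.
5. **General TMS procedures, navigation.** Guidance by the subject's anatomical MRI is the nearest thing to a barrier, because a refuser may have no such scan. But the sentence names single pulses, and the benefit claimed is accuracy: "The brain navigation system permits more precise TMS placement on the proposed anatomic regions". Nothing says that TMS is withheld without a scan, or that the scan must be later than the possible exposure to metal.
6. **General TMS procedures, motor threshold.** The coil is moved and the intensity varied "to find the site that most reliably elicits finger twitches". This can be done from the hand response alone, and use of the navigation system at this step is optional: "We may mark the stimulation sites in the neural navigation system".
7. **TMS sessions, measurements before each session.** MRI is planned before the session's TMS, so the metal question would normally come up first. But TMS-evoked responses, which themselves need pulses, belong to the same set of pre-session measurements, and the order within that set is not given. Nothing says what happens to TMS when the MRI is skipped.

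Result: step 1 stops MRI, and none of steps 1 to 7 states that TMS is stopped. Steps 5 and 7 make stimulation of such a person less likely without prohibiting it. Step 6 shows that motor-threshold pulses are the least protected.

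**The case against.** The strongest reply is that this argues from silence. The refusal sentence sits under an MRI heading and states an MRI consequence; it does not say that refusers go on to TMS. The TMS exclusion is categorical, and to apply it investigators must judge metal status. A refuser has already been flagged to them, and sensible staff would not stimulate. Navigation and the planned pre-session MRI also put an unsure refuser well off the intended pathway. Finally, General TMS procedures refers to inclusion criteria that are not listed in the available text, and consent pages were removed, so a TMS safety screen may exist elsewhere.

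Much of this stands. The practical barriers are real, and the absence of an eligibility list from the available text cannot be held against the plan. What does not stand is that the matter is silence alone. The protocol gives a specific instruction for this very participant, and the consequence it names is too narrow. The protection then depends on staff reading possible metal into an exclusion worded for actual metal.

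A reader might go further and infer that the protocol permits TMS in people with eye or skull metal, or that its MRI and TMS rules conflict. Neither is supported. Known metal is plainly excluded, and the two rules can both be followed; they simply leave unresolved status uncovered.

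**Conclusion.** The point holds as a minor safety correction, to be considered, with medium confidence. As written, the refusal rule closes MRI but not TMS to a participant whose possible eye or skull metal is unresolved, and no other visible rule closes it.

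Its size cannot be given. The documents report no frequency for uncertain metal status or for x-ray refusal, so the number affected is unknown and may be zero. A reader might try to size it by one participant's share of the planned sample of about 30, or by the minutes of active stimulation. Neither works: the first is the same for any participant, the second is the ordinary study dose, and neither measures the chance or severity of harm.

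The conclusion assumes that the available text is applied literally and that no stricter screen exists outside it. If such a screen is in use, what remains is to bring this wording into line with it.

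**What to change.** Make two edits, with matching consent text.

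1. In MRI procedures, keep the right to refuse and widen the consequence: *A participant may refuse the x-ray. Unless possible metal in the eye or skull has been ruled out by other adequate imaging taken after the possible exposure, a participant who refuses will not take part in the MRI or receive any TMS, including motor-threshold testing.*
2. In the TMS paragraph of Research Related Risks, extend the exclusion to people in whom possible metal inside the eye or skull has not been ruled out. This also covers an unsure participant who was never asked for an x-ray, since the request is discretionary.

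The investigators should state what counts as adequate imaging, so that staff do not have to decide case by case.

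The cost is a short wording amendment and the possible loss of a very few participants. There is also a cost to participants: for those who are unsure, an x-ray (a small radiation dose, as the protocol notes) or equivalent clearance becomes a condition of TMS, where at present the x-ray is tied only to MRI. That is reasonable, because the protocol already treats metal in these sites as a reason not to stimulate.

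### The only test named for active versus sham TMS is unpaired, although every participant has both sessions; how session order is set is also not stated

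*Combined protocol and SAP*

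**What the plan says.** Under Study Procedures, the paragraph on the TMS sessions (after EEG/ERP recording) describes a two-session, within-person design: "TMS will be given in 2 sessions in 2 different days that are separated by one or more days". It continues: "In one session you will receive active TMS. In another session you will receive sham TMS". Outcomes are taken four times per person: "TMS-evoked responses, brain waves, and MRI will be measured before and after each session to determine the TMS effects". Planned enrolment is about 30. Nothing in the document says which session comes first, or whether order is randomised, counterbalanced or fixed.

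The Statistical Analysis Plan has three statements that bear on this:

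- A general one: "We will examine the differences in performances of biomarkers in active TMS compared to sham TMS". No test or model is given.
- A covariate one: "We will explore effects of age, sex, baseline medication, cognition, smoking status, and functional measures on biomarkers", with significant findings to be adjusted for. Neither period nor session order is in the list.
- An exploratory one: "Exploratory analyses were conducted comparing active TMS vs. sham at different time points using independent-sample t-test". The same sentence adds a second analysis, "comparing baseline vs. post-TMS measurements using paired-sample t-tests", at p < 0.05. The plan states that all tests are two-tailed.

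Paired tests are therefore named only for before versus after TMS, and not for active versus sham.

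**The concern.** An independent-sample t-test assumes that the two sets of values come from different people. Here they come from the same people. Measurements on one person on two days are usually positively correlated, and the unpaired standard error ignores that. With balanced order the test is then too conservative: it rejects far less often than 5% when nothing is going on, and it misses moderate effects that a within-person analysis would find. Active versus sham is the only controlled contrast in this study, so the loss falls where it matters most.

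The second part is conditional. In a two-session design, practice, familiarity or fatigue can shift values from session 1 to session 2. The tasks are learned ones ("They are trained and then perform the tasks by responding, remembering, or recalling certain items and ignoring the other items"). Training and breaks reduce such a shift but need not remove it. If active TMS comes second more often than first, or the reverse, part of the shift is counted as a TMS effect unless period is in the model. The document fixes neither the order nor a period term.

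**Working it through.** **Inputs from the document.** Two sessions per person, one active and one sham; about 30 participants; two-sided tests at 0.05. The document gives no SD, correlation, effect size or power, so there is no figure of its own to reproduce.

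**Assumptions.** n = 30 complete pairs; outcome SD 1; between-session correlation ρ of raw values 0.5 to 0.7; session-1-to-session-2 shift 0.3 SD; true effect 0 or 0.5 SD; no carryover. Ranges run from ρ = 0.5 to ρ = 0.7.

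**Step 1. Unpaired test, raw values, order 15:15.**

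- The test takes the standard error as √(2/30) = 0.258. It rejects when the difference exceeds about 2.002 × 0.258 = 0.517 SD (58 df).
- The true standard error of the active − sham mean is √(2(1 − ρ)/30), which is 0.183 at ρ = 0.5 and 0.141 at ρ = 0.7.
- With no effect, the difference must lie 0.517/0.183 = 2.8 or 0.517/0.141 = 3.7 true standard errors from zero. Simulation (100,000 runs, 0.3 SD shift) gives an actual error of 0.6% to 0.1%. Without the shift it is 0.7% to 0.1%.
- With a 0.5 SD effect, the normal approximation is P(Z > (0.517 − 0.5)/0.183) = 46% at ρ = 0.5, and 45% at ρ = 0.7 with 0.141 in the denominator. Simulation agrees: 46% to 45%.

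**Step 2. Within-person analysis with a period term, same setting.** The estimate is the mean of the two sequence means of active − sham, on 28 df. The noncentrality is 0.5/0.183 = 2.74 or 0.5/0.141 = 3.54. Power is 75% to 93% and the error about 5%.

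**Step 3. Change scores.** Let the within-session correlation be 0.7 to 0.8, so the SD of change is √(2(1 − 0.7)) = 0.77 to √(2(1 − 0.8)) = 0.63. Order is 15:15 and the effect 0.5 SD.

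| Correlation of the two sessions' changes | Unpaired error | Unpaired power | Within-person power |
|---|---|---|---|
| 0 | about 5% | 69% to 85% | 67% to 84% |
| 0.3 | 2% | 72% to 89% | 82% to 94% |
| 0.5 | 0.7% | 75% to 93% | 93% to 99% |

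The gain from pairing therefore depends on the quantity compared. It is nil if changes are uncorrelated between sessions.

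**Step 4. Unbalanced order, raw values, no true effect.** If k of 30 receive active first, the bias is shift × (30 − 2k)/30.

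- k = 15: 0.3 × 0/30 = 0.
- k = 10 (20:10): 0.3 × 10/30 = 0.10 SD.
- k = 0 (one order for all): 0.3 × 30/30 = 0.30 SD.

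False positives of the unpaired test are 1.4% to 0.3% at 20:10 and 13% to 8% in one order. A paired test without a period term gives 7% to 8% at 20:10. Adding the period term at 20:10 gives bias 0 and about 5% error. In one order for all, period and treatment cannot be separated by any model.

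**The case against.** Four arguments on the other side have force.

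- **The t-test is only exploratory, and it errs on the safe side.** Both are true for raw values with balanced order. But the non-exploratory sentence then has no method at all, and a conservative test in about 30 people means missed effects.
- **Change scores may be what is meant.** Measurements are taken before and after each session. A reader might infer that nothing in the design guards against a session shift, but that is too strong: the pre-TMS values could cancel a stable day-to-day shift. What remains is that the plan does not commit to comparing change between sessions. Its reference to separate time points reads more naturally as raw values.
- **Silence on order is not a fixed order.** A reader might infer that order is fixed, or that the active-versus-sham estimate is biased. The wording on the two sessions is neutral, and order may well be randomised in practice. Step 4 is a conditional calculation. Even at 20:10 the unpaired test's false positives stay below 5%, so the harm there is bias in the estimate rather than excess false positives.
- **The size rests on assumed values.** This stands. The assumption of 30 complete pairs is also optimistic. Under MRI procedures, each subject does only part of the task set and may stay in the study with some tests missing, so pairs per biomarker may be fewer and the within-person powers lower. The figures also assume no carryover, although the gap between sessions may be as short as one day.

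A reader might also infer that the primary analysis is wrong. The plan labels no comparison main or primary. The narrower statement is that the only named active-versus-sham test does not fit the design.

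**Conclusion.** The mismatch is clear from the text: both conditions are given to each person, and the one named active-versus-sham test is for two separate groups. This should be corrected. If raw values are compared and order is balanced, the cost under the stated assumptions is a fall in power at 0.5 SD of about 29 points at ρ = 0.5 (75% − 46%) to 48 points at ρ = 0.7 (93% − 45%). If uncorrelated change scores are compared, the cost is nil.

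The unstated order is a secondary gap with conditional consequences. The document does not show that order is unbalanced or that any estimate is biased. Confidence in the mismatch is high; confidence in its size is moderate, because it depends on correlations and a session shift that the document does not give.

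**What to change.** **Statistical Analysis Plan.** Replace the independent-sample t-test with one within-participant analysis, and name it as the method for active versus sham. A mixed model with treatment and period as fixed effects and participant as a random effect is preferable, because it keeps participants with an incomplete pair. Fix in advance how each session's pre-TMS value enters, as a change score or as a covariate.

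**Study Procedures.** State that session order is randomised 1:1 (active then sham, or sham then active). Blocking is optional. Simple randomisation of 30 gives 20:10 or worse with probability 2 × P(Bin(30, 0.5) ≤ 10) = 9.9%, and the period term covers that case. The plan mixes future and past tense, so it is unclear whether sessions have begun. If they have, report the order actually used and adjust for period; this does not help if everyone had the same order.

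**Cost.** One randomisation list if order is still open, a sentence in each section, and about one degree of freedom (29 to 28, which leaves power at 0.5 SD and ρ = 0.5 at about 75%). No extra visits or participants are needed. There is little or no gain in power if changes are uncorrelated between sessions, and carryover is not removed.
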